6.10 Audio Visual Recordings

In order to create training videos for the raters, 6 patients at NYU Langone Medical Center and Shanghai Mental Health Center will be recorded (either audio or video) while interviewed with the

CONFIDENTIAL

BPRS, SANS, and CDSS (a total of 6 patients for each scale at each site). These patients will not need to participate in the rest of the study and do not need to meet inclusion criteria for the study. Participants will sign a separate consent form (audio/video training ICF) indicating that they consent for voice or audio recording and are volunteering to complete the assessment understanding that it will be used for rater training in this study or in future studies conducted under the supervision of [name]. In addition, patients recruited at NYU Langone Medical Center will sign the “Authorization for Use and Disclosure of PHI for Academic Purposes” form found on the Compliance Policies intranet site (<https://central.nyumc.org/shared/legal/compliance/Pages/Policies-and-Procedures-.aspx>) or in the HIPAA manual in Ellucid (<https://nyumc.ellucid.com/documents/view/4582/7653>), and the signed form will be maintained for a minimum of six (6) years. At NYU, participants will be recruited and consented in English or Mandarin, and assessments may be conducted in English or in Mandarin. Consenting research staff will be fluent in the language of consent (English or Mandarin) and will conduct the consent in either English or in Mandarin depending on the subject’s preferred language.

If participants enrolled in the study at NYU Langone Medical Center agree to have their assessments recorded, they will need to sign the audio/video training ICF, the Institution Authorization for use and Disclosure of PHI for Academic Purposes form in addition to the main study ICF and they will be compensated \$20 in addition to the compensation for the overarching study.

These recordings will be deidentified, labeled only with the subject’s study ID, and kept on a shared drive that is only accessible to individuals who are study staff within [name] lab. Only research staff who are directly involved in the study will have access to these files. Additionally, [name] PhD, an independent contractor, will also have access to the videos as she will primarily be responsible for the rater training for the study. [name] has served as the gold standard rater on previous studies for [name] and primary trainer for clinical assessments. As per [name] agreement, she will be covered as a contractor by HIPAA confidentiality rules. [name] will review audiovisual recordings behind the NYU firewall.

7 Statistical Plan

7.1 Analysis population

The modified Intent-to-Treat (mITT) population will be used for all efficacy endpoints. The mITT population includes all randomized subjects who receive one dose of study medication and at least one evaluation post baseline.

7.2.2 Secondary analyses

As a sensitivity analysis to the MAR assumption, if the trial retention rate at Week 12 is below 70%, a stratified analysis based on follow-up duration will be carried out.

If the treatment arm difference in BPRS continues to diverge, a parametric model will be added using "visit" as a continuous variable. The functional form of "visit" in the model shall be selected among linear, linear + logarithm spline term, linear + exponential spline term to properly capture the trajectories. A significant interaction term will be a more effective evidence than AUC difference between treatment arms.

7.4 Tertiary Endpoint Analyses

A linear regression model on hippocampal volume change from baseline to Week 12 with following predictors will be built to explore the potential mechanism: duration of untreated psychosis, levetiracetam blood level at week 6, and serum biomarkers for oxidative stress (thioredoxin) and astroglial injury (S100B).

The Spearman Correlation will be calculated for following pairs of variables with two treatment arms pooled together:

- MATRICS composite score change from baseline to Week 12, and hippocampal volume change from baseline to Week 12;
- Modified SANS total score change from baseline to Week 12, and hippocampal volume change from baseline to Week 12;

CONFIDENTIAL

- BPRS total score change from baseline to Week 12, and hippocampal volume change from baseline to Week 12;
- MATRICS composite score change from baseline to Week 12, and pre-dose hippocampal blood flow change from baseline to Week 12;

Modified SANS total score change from baseline to Week 12, and pre-dose hippocampal blood flow change from baseline to Week 12;

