5. Levetiracetam's effects on cognition and symptoms will be associated with its effects on hippocampal volume.
6. Levetiracetam's effects on cognition and symptoms will be associated with baseline hippocampal CBF and change from baseline in hippocampal CBF
7. Duration of untreated psychosis and serum biomarkers for oxidative stress (thioredoxin) and astroglial injury (S100B) will predict hippocampal volume loss.

CONFIDENTIAL

8. Change from baseline to week 12 in hippocampal CBF will be associated with week 6 levetiracetam blood level and change in BPRS total score.

3 Study Design

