7.5 Sample Size Determination

A sample size of 84 randomized in a 2:1 ratio of levetiracetam to placebo provides 80% power to detect a moderate effect size (Cohen's d of 0.65) with a two-sample t-test and two-sided level of significance at $p=0.05$.

With no missing data, the primary analysis is equivalent to a two-sample t-test on AUC estimates. With a 2:1 randomization ratio, the effect size can be calculated as:

$$d = \frac{\delta_{AUC}}{\sigma_{AUC}} = \sqrt{\frac{3}{2 \times N_{control}}} (Z_{\alpha/2} + Z_{\beta}) = \sqrt{\frac{3}{56}} (1.96 + 0.84) = 0.648$$

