7.6 Subject Population(s) for Analysis

Both the incidence of adverse effects and ASL evidence of hippocampal target engagement will be analyzed in all participants who receive study drug. The primary efficacy outcome measure for this trial are described above in section 3.2.

The modified Intent-to-Treat (mITT) population will include all randomized subjects who receive one dose of levetiracetam and at least one evaluation post baseline.

8 Safety and Adverse Events

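### The tertiary regression of hippocampal volume change includes levetiracetam blood level but no treatment-arm term, so in a two-arm fit its level coefficient cannot separate drug versus placebo from a concentration effect

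*Protocol*

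**What the plan says.** Section 7.4 describes the model in one sentence: "A linear regression model on hippocampal volume change from baseline to Week 12 with following predictors will be built to explore the potential mechanism". The predictors are "duration of untreated psychosis, levetiracetam blood level at week 6, and serum biomarkers for oxidative stress (thioredoxin) and astroglial injury (S100B". Treatment arm is not among them, and the sentence names no population.

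The next sentence of 7.4, on the correlations, does say what happens to the arms: "The Spearman Correlation will be calculated for following pairs of variables with two treatment arms pooled together". Section 7.3 likewise has its correlation of blood flow change with BPRS change disregard treatment assignment.

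The analysis population is defined twice. Section 7.1 says the mITT set "includes all randomized subjects who receive one dose of study medication and at least one evaluation post baseline". Section 7.6 says it "will include all randomized subjects who receive one dose of levetiracetam and at least one evaluation post baseline".

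Among the tertiary hypotheses in section 2, number 7 names untreated-psychosis duration, thioredoxin and S100B as predictors of volume loss and does not mention drug level. Number 8 brings in the level for a different outcome: the change in hippocampal blood flow "will be associated with week 6 levetiracetam blood level and change in BPRS total score".

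**The concern.** A placebo participant has a levetiracetam level of essentially zero, so in a two-arm fit the level variable carries treatment assignment as well as concentration. Secondary hypothesis 2 expects an arm difference in this same outcome, namely less volume loss on levetiracetam. If that is true, the level coefficient is expected to be non-zero even when concentration is irrelevant among those who took the drug.

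The model's stated purpose is to explore mechanism, and section 7.3 already covers the plain arm comparison. A reader would therefore take a significant level coefficient as evidence that higher concentrations protect volume. The model as listed cannot support that inference. At stake is the interpretation of one exploratory coefficient, and of any similar analysis of blood flow against level.

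**Working it through.** **The plan's own figure.** Section 7.5 states that "A sample size of 84 randomized in a 2:1 ratio of levetiracetam to placebo provides 80% power" for a "moderate effect size (Cohen's d of 0.65". With 28 controls, √(3/56) × (1.96 + 0.84) = 0.648. Solving for d = 0.65 returns 28 controls and 84 in total; power is 0.802 by the normal approximation and 0.793 by the noncentral t. The figure reproduces, but it concerns BPRS. The protocol gives no treatment effect on hippocampal volume, so d = 0.65 is borrowed below only as an illustration.

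**Which participants enter.** The regression sentence does not say. Four things point to both arms:

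- the two-arm mITT definition in 7.1;
- the pooling of arms in the adjoining correlations;
- the arm-blind correlation in 7.3;
- the pilot in section 1.3, which reports level against perfusion change as r = −0.51, p = 0.04. An ordinary correlation test gives p ≈ 0.04 with all 17 analysed participants, but about 0.075 with 13, the most that the two levetiracetam groups could supply (6 on 500 mg; 7 on 185 mg, where one participant was 14%).

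Against this stands 7.6, which taken literally would remove placebo from every mITT comparison and so looks like a slip.

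**How level and arm overlap.** Let p = 2/3 be the levetiracetam share, m the mean level on drug, c its CV, and the placebo level 0. Then:

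- Cov(arm, level) = p(1 − p)m
- Var(level) = p m²[(1 − p) + c²]
- Between-arm share of level variance: R = (1/3) / (1/3 + c²)

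With an arm effect d, no within-arm relation, and other predictors independent of level, the expected level slope without an arm term is d × R / m. Multiplied by m, this is the apparent effect at the mean treated level, d × R. It shrinks as c grows but never reaches zero.

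| Level CV (assumed) | R | Apparent effect, 0.65 × R |
|---|---|---|
| 0.3 | 0.79 | 0.51 |
| 0.5 | 0.57 | 0.37 |
| 0.7 | 0.40 | 0.26 |
| 1.0 | 0.25 | 0.16 |

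R passes one half at c = √(1/3) = 0.577. If 10% of treated participants have a zero level, R falls to 0.61, 0.46 and 0.34 at CV 0.3, 0.5 and 0.7.

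**How often the level term is significant.** Simulation used log-normal levels on drug, zero on placebo, three independent covariates, arm effect 0.65, no within-arm relation, two-sided 0.05 and 3,000 runs per cell. MRI is optional in this trial, so 42 scanned participants are shown beside 84.

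| Level CV | 84 (56:28), no arm term | 42 (28:14), no arm term | With arm term, either size |
|---|---|---|---|
| 0.3 | 67% | 38% | about 5% |
| 0.5 | 54% | 30% | about 5% |
| 0.7 | 42% | 22% | about 5% |
| 1.0 | 30% | 16% | about 5% |

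Repeat runs move these by one or two percentage points. With no arm effect at all, the model without an arm term also rejects at about 5%, so the excess comes from the arm contrast.

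The mixing works in the other direction too. With a within-arm slope of 0.4 outcome SD per SD of level and no average arm difference, at 84 participants, the model as listed detects the slope in 27% to 60% of trials over the same CVs. With an arm term it does so in 75% to 81%.

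**The case against.** The strongest reply is that the protocol never says both arms enter, and that the population and full covariate list of an exploratory model are often left to a statistical analysis plan, which is not at hand. The first part stands: pooling is an inference, though the better supported one. The second stands only in part, because 7.4 does list the model's predictors, and the list as written is the problem.

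A second reply is that the protocol does not call this an exposure-response test and that hypothesis 7 does not mention level, so the term may be a simple exposure adjustment. That is fair as to the label. It does not remove the ambiguity of a blood-level coefficient in a model offered as evidence on mechanism.

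A third is that the arm effect on volume may be small. Section 1.3 reports no volume loss in the 12 months after initial stabilisation on antipsychotics, and this trial requires at least 8 weeks of prior treatment. That limits how large the distortion may be in practice; it does not make the coefficient interpretable.

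Three stronger readings are tempting and should be resisted:

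- A reader might infer that the level coefficient mainly re-tests drug versus placebo. That needs a level CV below about 0.58 and few zero levels. The protocol gives no CV. Samples are pre-dose and the stated half-life is 6–8 hours, so wide variation is plausible.
- A reader might infer that any drug effect on volume would appear as a concentration effect. The simulated rates, 16% to 67% even at d = 0.65, do not support that.
- A reader might think the week-12 level should replace the week-6 one. Week 6 is the midpoint of the period over which the change accrues, and hypothesis 8 names it. The choice is defensible, and a single week-12 trough would reflect recent dosing just as narrowly.

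**Conclusion.** The point holds in limited form. As listed, and fitted in both arms, the model cannot tell a drug-versus-placebo difference from a concentration effect. The size rests on assumed inputs: an arm effect of 0.65 SD on volume, no within-arm relation, placebo levels at zero, and a level CV between 0.3 and 1.0. On those, the level term is significant three to thirteen times as often as the nominal 5% (16/5 ≈ 3; 67/5 ≈ 13), and an arm term brings it back to nominal. If the model were fitted in levetiracetam participants only, the problem would not arise, but the protocol does not say so. Severity is minor, since no primary or secondary conclusion depends on this model.

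**What to change.** In section 7.4, state which participants enter the regression. One option is to include both arms and add treatment arm as a predictor, which keeps the placebo data for untreated-psychosis duration, thioredoxin and S100B. The other is to estimate the level term in levetiracetam participants only. Apply the same rule to any analysis of blood flow change against level under tertiary hypothesis 8, for which sections 7.3 and 7.4 currently list none. Reconcile the mITT wording in 7.1 and 7.6 at the same time, since it bears on who enters.

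The week-6 level can stay. The change is to analysis wording only and needs no new data or visits. The cost is a less precise level coefficient, because it then draws only on variation among treated participants.

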7.5 Sample Size Determination

A sample size of 84 randomized in a 2:1 ratio of levetiracetam to placebo provides 80% power to detect a moderate effect size (Cohen's d of 0.65) with a two-sample t-test and two-sided level of significance at $p=0.05$.

With no missing data, the primary analysis is equivalent to a two-sample t-test on AUC estimates. With a 2:1 randomization ratio, the effect size can be calculated as:

$$d = \frac{\delta_{AUC}}{\sigma_{AUC}} = \sqrt{\frac{3}{2 \times N_{control}}} (Z_{\alpha/2} + Z_{\beta}) = \sqrt{\frac{3}{56}} (1.96 + 0.84) = 0.648$$

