This material is the property of the NYU School of Medicine and Langone Medical Center. Do not disclose or use except as authorized in writing by the study sponsor

Study Summary

Title	A 12 week randomized, double-blind, placebo-controlled trial investigating the effects of levetiracetam in early psychosis
Protocol Number	S19-01820
Study Duration	
Months 1-6: Complete regulatory requirements for the R33 trial, train staff at both sites, verify inter-rater reliability and calibrate MRI morphometry between sites. Complete initiation visit at Shanghai Mental Health Center (SMHC). Complete data collection and data management systems.
 
Months 6-29: Enroll 3 subjects per month at SMHC and 1.5 subjects per month at NYUMC to complete the enrollment target of 84 participants in month 26 and last participant completed in month 29. Repeat inter-rater reliability testing and training every 6 months and site visits annually.
 
Months 30-36: Data analysis and manuscript preparation.

Study Center(s)	
Multicenter Study:
 
New York University Langone Medical Center /Bellevue Shanghai Mental Health Center (SMHC)

Objectives	The objectives of this study are to evaluate the efficacy of 12 weeks of Levetiracetam (500 mg) twice daily versus placebo on clinical symptoms, hippocampal volume and cognition and tolerability when added to antipsychotic in early psychosis (EP) patients with treatment-resistant symptoms and to assess the association between hippocampal cerebral blood flow (CBF) and markers of oxidative stress and inflammation with outcomes.
Endpoints / Outcome Measures	
84 treatment resistant early psychosis (EP) subjects will be studied in a two-site, 12-week, double-blind, placebo-controlled trial of levetiracetam 500 mg twice daily added to a stable dose of clinician-determined antipsychotic..
 
 - Change in BPRS total score at 12 weeks is the primary outcome; - Hippocampal volume change measured by MRI prior to the first dose and after 12 weeks and hippocampal CBF measured by arterial spin labeling (ASL) are the secondary outcomes. - In addition, we will measure other clinical symptoms and cognition and will analyze levetiracetam blood levels and biomarkers for oxidative stress and glial injury that predicted hippocampal volume loss in our previous study.

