5.3 Method for Assigning Subjects to Treatment Groups

Randomization will be in a 2:1 ratio in blocks of random size (3 or 6), stratified by site based on the median value for each site from our previous studies.

Preparation and Administration of Study Drug:

At NYU, study drug dispensation will take place at the NYU Langone Investigational Pharmacy. In order to ensure blinding, the 500mg and placebo will be prepared in identical capsules. Once a participant passes the screening procedures, the Investigator or study MD or NP will enter the prescription information into EPIC or write a prescription order to be submitted physically to the pharmacy. The study drug will be prepared in accordance with the randomization list which will be kept by the pharmacy. Study staff will retrieve the study drug from the pharmacy and the either an inpatient MD or NP or a study MD or NP will dispense the drug. Preparation and dispensation of study drug at SMHC will be performed by the SMHC research pharmacy.

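### The 80% power in section 7.5 holds only with complete data on all 84 randomised patients; no expected retention is stated and no allowance is made for dropout or mITT exclusions

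*Protocol*

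**What the plan says.** Protocol section 7.5 opens: "A sample size of 84 randomized in a 2:1 ratio of levetiracetam to placebo provides 80% power to detect a moderate effect size". The effect is specified as a "moderate effect size (Cohen's d of 0.65) with a two-sample t-test" at two-sided 5%. The formula that follows puts in 28 controls, which is every control that 84 patients at 2:1 can supply. The sentence before the formula gives its condition: "With no missing data, the primary analysis is equivalent to a two-sample t-test on AUC estimates".

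The Study Summary plans accrual "to complete the enrollment target of 84 participants in month 26", so the number in the power formula is also the number to be enrolled. No expected dropout rate, inflation factor or power after loss is given in section 7.

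Elsewhere the plan provides for loss:
- Section 7.1 limits the efficacy population to randomised patients with a dose and at least one post-baseline evaluation.
- Section 7.2.2 adds a stratified sensitivity analysis "if the trial retention rate at Week 12 is below 70" per cent. Section 7.3 calls for multiple imputation in a correlation analysis at the same threshold.
- Section 7.2.1 expects dropout to matter little under missing at random, and gives no figure.

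**The concern.** The opening sentence of 7.5 attaches 80% power to the number randomised, while the calculation behind it needs the same number with complete data. The design has no spare power, so any loss takes it below the stated value. This is the only power statement in the protocol, and it justifies N for the primary BPRS endpoint. A reader of a null result would take 80% power at d = 0.65 as the sensitivity of the trial, and could not tell from the document how far attrition and mITT exclusions had reduced it.

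**Working it through.** **Inputs from the protocol.** N = 84, allocation 2:1 (section 5.3: "Randomization will be in a 2:1 ratio in blocks of random size (3 or 6), stratified by site"), hence 56 and 28; d = 0.65; two-sided alpha 0.05; BPRS at weeks 0, 2, 3, 4, 6, 8 and 12; random intercept plus spatial-power residual covariance (section 7.2.1).

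**Step 1: the plan's figure.** Detectable d = sqrt(3/56) x (1.96 + 0.84) = 0.648, as printed. The noncentrality at d = 0.65 is 0.65 x sqrt(28 x 56/84) = 2.81.
- Normal formula: Phi(2.81 - 1.96) = 80.2%.
- Exact noncentral t, 82 degrees of freedom: 79.3%; d detectable with 80% power is 0.656.

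The figure stands for complete data, with no reserve.

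**Step 2: lower bound.** Suppose dropouts contribute nothing and losses are equal in the two arms. The noncentrality is then multiplied by sqrt(retention). At 70%, 2.81 x sqrt(0.7) = 2.35, which gives 65.2% (normal) or 63.7% (exact t).

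**Step 3: the planned model.** Trapezoid weights derived from the visit weeks are [1, 1.5, 1, 1.5, 2, 3, 2]/12. For each dropout pattern I computed the generalised-least-squares variance of this contrast and divided the complete-data variance by it. This is the relative efficiency RE. Power then follows from 2.81 x sqrt(RE), by t with 84 x RE - 2 degrees of freedom.

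Assumptions not in the protocol: random-intercept share of variance 0 to 0.7, weekly correlation 0.5 to 0.9, monotone missing-at-random dropout with the same pattern in both arms. In the spread pattern, the last visits of those lost are divided evenly over weeks 2 to 8.

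Exact-t power at d = 0.65:

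| Retention | Dropouts contribute nothing | RE, loss spread | Power, loss spread | Power, all loss after week 2 |
|---|---|---|---|---|
| 90% | 74.8% | 0.949-0.995 | 77-79% | 76-79% |
| 80% | 69.7% | 0.896-0.988 | 75-79% | 72-78% |
| 70% | 63.7% | 0.840-0.981 | 72-79% | 67-78% |

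The normal formula gives values about one point higher, for example 73-79.5% at 70% retention with loss spread.

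**Step 4: mITT exclusions.** If one third of those lost have no post-baseline rating, and so leave the analysis entirely, the normal formula gives 77-79%, 74-77% and 71-75% at 90%, 80% and 70% retention.

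**Step 5: detectable effect.** Dividing 0.656 by sqrt(RE) at 70% retention with loss spread gives 0.656/sqrt(0.981) = 0.66 to 0.656/sqrt(0.840) = 0.72. In the lower-bound case it is about 0.74 at 80% retention and 0.79 at 70%.

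**The case against.** The strongest reply is that nothing is miscalculated or hidden. The 80% reproduces, the no-missing-data condition is printed beside the formula, and section 7.2.1 argues that frequent ratings over a short period limit the effect of dropout. With seven visits in the mixed model, a patient with any post-baseline rating contributes, and in the milder scenarios the shortfall is only one to three points. A null result would in any case be read mainly from its confidence interval. All of this stands, and it makes the point minor.

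What remains is that the opening sentence of 7.5 carries no condition, section 7.2.1 puts no size on its claim, and patients outside the mITT set are lost completely whatever the model.

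Two stronger readings are tempting, and the documents support neither. A reader might infer from the 70% threshold that the sponsor expects such retention. It is a trigger for extra analyses, and no expected rate is given anywhere. A reader might also take 64-70% as the trial's real power. Those figures discard every rating from patients who drop out, which contradicts the planned analysis.

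**Conclusion.** The point holds as a minor one. The 80% is correct for complete data on every randomised patient and is not delivered under any loss. It is an incomplete planning figure and not an error of arithmetic.

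Under the planned model with loss spread over follow-up, the shortfall from the stated 80% runs from about one point up to about eight points at 70% retention. It reaches about thirteen points at 70% if all losses follow week 2 and within-patient correlation is weak. These sizes rest on assumed covariance, dropout patterns and retention rates, none of which the protocol gives. They show a range and do not predict this trial's power. They also assume missing at random; informative dropout would raise a question of bias that power figures do not address.

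**What to change.** Keep N at 84 and revise section 7.5 in three respects:
1. Say that about 79-80% power at d = 0.65 is the complete-data figure.
2. State the retention that the sponsor expects at week 12, and the share of randomised patients expected to fall outside the mITT set.
3. Give the power and the detectable effect of the mixed-model AUC at that retention, with the covariance and dropout assumptions shown as a range.

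The ranges above should not be copied in as fixed values, because their inputs are not the sponsor's. Inflating N to secure 84 completers (84/0.8 = 105 at 20% loss, for example) is not needed for this correction and would ignore the information that the model recovers from partial follow-up.

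The cost is a few sentences and one short calculation. The stated power becomes slightly less favourable; sample size, design and primary analysis do not change.
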